#### 1165 **4.5.1. Study Methods**

This is a prospective cohort study of patients with chronic HCV undergoing LDLT.
Contemporaneous DDLT recipients matched (as in main prospective study) will be used
as controls. Potential DDLT recipients listed for liver transplantation who are likely to be
transplanted within the next 3 months will be approached and consented for study. The
primary endpoint of the study is the severity and rate of histological disease progression.
Antiviral therapy will not be used until the patient achieves a level of significant disease

severity that has been defined by four histological endpoints with/without clinical criteria.
Protocol biopsies at 3 months and annually will be used to assess rate of recurrence and
severity of disease. Patients will be followed for up to 3 years. Data and specimens will

1175 be collected to evaluate the effect of specific clinical, virological and immunological

- factors on disease progression in LDLT recipients and controls.
- 1177

1182

1186

1187

1190

1191

1193

1194

## 1178 **Study Endpoints**

1179 The primary and some of the secondary endpoints are based upon liver histology. Any 1180 liver biopsy performed post-transplantation will be reviewed for the HCV histological 1181 endpoints (i.e. both protocol biopsies and biopsies done as part of clinical care).

#### 1183 **Primary Endpoint**

- Proportion of patients with one of the following four endpoints indicative of "progressive" disease:
  - a. Ishak fibrosis score of  $\geq 3$  (some bridging fibrosis)
  - b. Ishak fibrosis score of  $\geq 2$  plus total bilirubin > 5.0 mg/dL
- 1188c. Ishak fibrosis score of  $\geq 2$  plus Knodell score (necroinflammatory indices)1189 $\geq 9$ 
  - d. Diagnosis of cholestatic hepatitis
- 1192 Additional causes of liver test elevation must be excluded. Specifically, there must be:
  - e. Absence of rejection (acute and chronic)
    - f. Absence of biliary disease

1195	g. Sepsis
1196	
1197	Secondary Endpoints
1198	1. Rate of fibrosis progression (Ishak fibrosis score) – change in fibrosis score per
1199	year
1200	2. Total and necroinflammatory scores at 3 months, 1 year, 2 years and 3 years
1201	(Knodell score)
1202	3. Time to recurrence of disease determined by proportion of patients with
1203	histological evidence of recurrent HCV at 3 and 12 months
1204	4. Viral level at day 7 and months 1, 3, and 12, 24 and 36– comparison of LD and
1205	DDLT recipients and prediction of post-LT disease progression.
1206	5. Proportion with cholestatic hepatitis
1207	6. Graft and patient survival
1208	
1209	4.5.2. Participant Selection
1210	See Section 4. for general eligibility criteria, and Section 4.2.2 for further details on
1211	selection of contemporaneous controls.
1212	4.5.3. Data Elements
1213	Potential Recipients positive for HCV
1214	1. HCV at enrollment
1215	2. HCV survey
1216	
1217	Recipients positive for HCV
1218	1. HCV intraoperative sample collection
1219	2. HCV at Transplant
1220	3. HCV Post-operative Recurrence and Rx data
1221	4. Liver biopsy and histology data
1222	
1223	Histological Evaluation:
1224	Local pathologists will use a standardized form for scoring all liver biopsies on HCV
1225	study participants performed after the first 4 weeks post-transplantation. The Knodell
1226	system (See Appendix R) will be used. To be an evaluable biopsy, in terms of HCV-
1227	related endpoints, there must be an absence of other concurrent conditions such as acute
1228	rejection, biliary obstruction and CMV hepatitis. Both protocol liver biopsies (month 3
1229	and annually) and non-protocol biopsies will be scored for evidence of HCV recurrence.
1230	4.5.4. Sample Size and Power Calculations
1231	We estimate the total number of transplant patients available (based on the recent survey
1232	of A2ALL transplant centers) to be 360 LDLT and 355 DDLT. We assume that 30% of
1233	waitlist patients have HCV, or approximately (0.30*360=) 108 LDLT and (0.30*355=)
1234	107 DDLT. All calculations below assume two-sided testing with a significance level of
1235	0.05.

- 1237 1. The primary endpoint upon which the study will be powered is histological severity of 1238 disease at 1 year. We base sample size calculations on a comparison of binomial 1239 proportions. If we assume that 10% of DDLT patients achieve the composite endpoint of 1240 (Ishak  $\geq$ 3, etc), we have 82% power to detect an increase in the LDLT proportion to 25%.
- 1240

1242 2. The secondary endpoints also capture rate of disease progression. If we assume 50%

1243 of DDLT patients will achieve the composite endpoint at 3 years, we will have 85%

1244 power to detect an increase in the LDLT proportion to 70%. Thus, based on dichotomous

1245 endpoints (progression or not), we can only detect a difference between LDLT and

- 1246 DDLT with high power only if the difference is at least 15-20%.
- 1247

1248 Alternatively, we can look at differences in fibrosis progression using a numeric scale.

1249 With an estimate of SD=0.25 for the yearly rate of increase in fibrosis score, we have

1250 82% power to detect an increase or decrease of 0.10 compared to 0.45 (DDLT)

- 1251 [Berenguer 2000 -- for DDLT 0.3-0.48/year on Desmet scale 0-4)]. Power will be
- 1252 greater to detect LDLT rates above 0.55 or below 0.35.
- 1253
- 1254

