## 4.5.5. 4.5.5 Statistical Analysis

The primary objective is to compare HCV progression probabilities in LDLT versus DDLT, where HCV progression is defined above. This comparison will be tested using logistic regression, with HCV progression (yes/no) at a given time point as the outcome variable, and LDLT versus DDLT as the covariate of interest. This comparison will be adjusted for other variables associated with HCV progression. If HCV progression is evaluated at regular points over time, then discrete time survival analysis will be used to compare the time until HCV progression in the two groups.

1262

1263 Secondary objectives will involve several analyses. First, both the rate of fibrosis 1264 progression (change in Ishak score over time) and change in the necroinflammatory score 1265 (Knodell score) will be analyzed using repeated measures regression. A difference in 1266 slopes of the Ishak or Knodell scores over time for LDLT and DDLT will be tested with 1267 an interaction term between LDLT/DDLT and follow-up time. Second, the proportion of 1268 patients with histologic evidence of recurrent HCV at 3 months and 1 year after LDLT 1269 versus DDLT will be compared using logistic regression. This analysis will parallel the 1270 analysis for the primary objective described above. Because recurrent disease occurs 1271 prior to progressive disease, these two analyses will not be independent. Third, analysis 1272 of viral level at day 7 and months 1, 3, 6, and 12 will be performed using repeated 1273 measures regression, with the primary comparison between LDLT and DDLT. 1274 Differences in the pattern of viral levels over time will be tested using a time by 1275 LDLT/DDLT interaction. As a second step, HCV disease severity will be added to the 1276 model to see if viral level is significantly predicted by disease severity. Fourth, the 1277 incidence of cholestatic hepatitis in LDLT and DDLT will be compared using logistic 1278 regression, adjusted for any other prognostic factors. Finally, graft and patient survival 1279 will be analyzed using Kaplan-Meier estimators, logrank tests comparing LDLT and 1280 DDLT, and Cox regression to compare groups adjusted for other variables.

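### The HCV biopsy scoring rule (Protocol 4.5.3) names only the Knodell system, but three of the four primary HCV endpoint components and the fibrosis-rate endpoint need an Ishak fibrosis score

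*Protocol*

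**What the plan says.** **Reading rule (4.5.3, Histological Evaluation).** "Local pathologists will use a standardized form for scoring all liver biopsies on HCV" participants, for biopsies after the first four weeks. The sentence that follows names the scale: the Knodell "system (See Appendix R) will be used". No other scoring system appears in that paragraph.

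**Primary endpoint (4.5.1, Primary Endpoint).** A patient counts as progressive if any one of four components is met:
- a: Ishak fibrosis of at least 3, glossed as "some bridging fibrosis"
- b: Ishak fibrosis of at least 2 "plus total bilirubin > 5.0 mg/dL"
- c: Ishak fibrosis of at least 2 "plus Knodell score (necroinflammatory indices") of at least 9
- d: "Diagnosis of cholestatic hepatitis"

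**Secondary endpoints (4.5.1).** The first is "Rate of fibrosis progression (Ishak fibrosis score"), expressed as change per year. The second is the Knodell total and necroinflammatory scores.

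**Analysis (4.5.5).** Ishak carries fibrosis and Knodell carries necroinflammation. A difference in "slopes of the Ishak or Knodell scores over time for LDLT and DDLT will be tested with" a group-by-time interaction.

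**General instruction (4.5.1, Study Endpoints).** Every biopsy taken after transplant, whether scheduled or prompted by clinical care, is to be checked against the histological HCV endpoints. No scale is named.

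**The concern.** The only sentence telling pathologists which system to apply points to a different scale from the one on which most of the primary endpoint is built. If a site takes 4.5.3 at its word, the slide yields a Knodell reading and no Ishak stage. Components a, b and c and the fibrosis slope would then be missing, or filled by applying Ishak cut-offs to a score from another scale. Readings are local at nine centres, and Section 4.5 mentions no central reading, so a site's own interpretation would pass straight into the endpoint. A later analysis plan cannot recover a stage that was never recorded.

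The same four endpoints appear in 4.5.1 (Study Methods) as the severity level before which antiviral therapy is not used. That text relies on the same stage, so it must be reconciled with the scoring rule. No clinical rule is proposed here.

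**Working it through.** **1. The plan's own figures.** 4.5.4 assumes 107 DDLT and 108 LDLT patients with HCV and a two-sided 0.05 level. For proportions, power = Φ[(|p2 − p1| − 1.96·SE0)/SE1], with SE0 pooled and SE1 unpooled.

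- Primary endpoint at 1 year, 10% vs 25%: pooled proportion (10.7 + 27)/215 = 0.175; SE0 = 0.0519; SE1 = 0.0508; (0.15 − 0.1017)/0.0508 = 0.95; power 83.0%. The plan states 82%. Other versions give 84.0% (unpooled), 84.1% (arcsine) and 77.9% (continuity-corrected).
- Composite at 3 years, 50% vs 70%: SE0 = 0.0668; SE1 = 0.0654; (0.20 − 0.1309)/0.0654 = 1.06; power 85.4%. The plan states 85%.
- Fibrosis rate, difference 0.10 with SD 0.25: 0.10/(0.25 × √(1/107 + 1/108)) = 0.10/0.0341 = 2.93; 2.93 − 1.96 = 0.97; power 83.5% (83.1% with the t distribution). The plan states 82%.

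All three reproduce closely. None depends on which scale the pathologist records, so the point is not numerical.

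**2. What each endpoint needs, against what 4.5.3 names.**

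| Endpoint | Ishak fibrosis | Knodell | Other | Fully covered by the scale named in 4.5.3? |
|---|---|---|---|---|
| Primary a | at least 3 | – | – | No |
| Primary b | at least 2 | – | bilirubin | No |
| Primary c | at least 2 | at least 9 | – | In part |
| Primary d | – | – | cholestatic hepatitis | Needs neither scale |
| Secondary 1, fibrosis rate | change per year | – | – | No |
| Secondary 2, total and necroinflammatory scores | – | yes | – | Yes |

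Three of four primary components and one of these two secondary endpoints need a score that the reading rule does not name.

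**3. Are the two names used interchangeably?** No. Component c requires both in a single criterion, and 4.5.5 models them as two outcomes. No conversion is given.

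**4. Does other text settle it?** No. Objective 2 in Section 3.5 cites reference 3 for the Ishak fibrosis score. Reference 3 is a 1981 paper on a numerical histological activity score whose author line carries both scale names, so the citation does not separate the two. The planning fibrosis rate in 4.5.4 is quoted on a third scale, Desmet 0–4.

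**The case against.** The best defence is the Study Endpoints text in 4.5.1. If every biopsy is checked against the HCV endpoints, and those are written in Ishak terms, the reader must assess Ishak fibrosis. The analysis in 4.5.5 also presupposes that Ishak scores exist. The reading detail sits on a standardized form and in Appendix R, neither of which is in the text at hand, and Section 8 places data element definitions in the Manual of Operations. An Ishak field may already be there.

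Much of this stands. A reader might infer that the primary endpoint cannot be derived at all. The documents do not support that: the Study Endpoints text points the other way, unseen material cannot be counted as missing, and component d needs no Ishak score. What the defence does not do is remove the conflict. The Study Endpoints text gives a purpose without a scale, and the sentence that does give a scale leaves Ishak out.

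Two further inferences also fail:
- **Loss of power.** Any such figure needs an assumed accuracy for improvised staging. The documents give none, and nothing shows that any centre would improvise.
- **Bias between groups because the LDLT:DDLT ratio runs from 1:100 to 1:3 (4.2.1).** That ratio describes the centres' activity. Section 4.2.2 requires comparable LDLT and DDLT numbers within each centre, reviewed every six months, and 4.5.2 refers HCV control selection to that section. The balance is set for the whole cohort and not for the HCV subset specifically, but the raw ratio is still the wrong figure to use.

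**Conclusion.** The concern holds as an internal conflict in how the primary HCV endpoint is measured: 4.5.3 names only Knodell, while components a, b and c and the fibrosis-rate endpoint require Ishak. This is a stated rule at odds with a stated endpoint, so it goes beyond detail that could be left to an analysis plan. It is confined to Secondary Aim 1, and no stated power or sample size changes.

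The practical effect depends on one unknown. If the form already has an Ishak field, only the wording of 4.5.3 is wrong. If it does not, the histological data for three of the four primary components are at risk for the planned 107 + 108 = 215 patients with HCV.

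**What to change.** Amend 4.5.3 to say that each HCV biopsy covered by the rule is staged for fibrosis on the Ishak scale and graded for necroinflammation on the Knodell indices, with the two entered as separate fields on the standardized form.

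State that the fibrosis part of components a, b and c, and the fibrosis slope, come from the Ishak field. Component b keeps its bilirubin criterion and component c its Knodell criterion, so the endpoint definition does not change. Reconcile the antiviral-therapy text in 4.5.1 with the amended scoring rule.

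Check whether any biopsies have been read without an Ishak stage. If so, the same local pathologist adds it from the existing slides.

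The cost is one sentence and at most one extra form field, with no new biopsy and no new reader. Any restaging is limited to slides found to lack the stage; the documents do not show whether there are any.

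It would also help to check that the source cited for the Ishak score in Section 3.5 is the one intended.

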## 4.5.5. 4.5.5 Statistical Analysis

The primary objective is to compare HCV progression probabilities in LDLT versus DDLT, where HCV progression is defined above. This comparison will be tested using logistic regression, with HCV progression (yes/no) at a given time point as the outcome variable, and LDLT versus DDLT as the covariate of interest. This comparison will be adjusted for other variables associated with HCV progression. If HCV progression is evaluated at regular points over time, then discrete time survival analysis will be used to compare the time until HCV progression in the two groups.

1262

1263 Secondary objectives will involve several analyses. First, both the rate of fibrosis 1264 progression (change in Ishak score over time) and change in the necroinflammatory score 1265 (Knodell score) will be analyzed using repeated measures regression. A difference in 1266 slopes of the Ishak or Knodell scores over time for LDLT and DDLT will be tested with 1267 an interaction term between LDLT/DDLT and follow-up time. Second, the proportion of 1268 patients with histologic evidence of recurrent HCV at 3 months and 1 year after LDLT 1269 versus DDLT will be compared using logistic regression. This analysis will parallel the 1270 analysis for the primary objective described above. Because recurrent disease occurs 1271 prior to progressive disease, these two analyses will not be independent. Third, analysis 1272 of viral level at day 7 and months 1, 3, 6, and 12 will be performed using repeated 1273 measures regression, with the primary comparison between LDLT and DDLT. 1274 Differences in the pattern of viral levels over time will be tested using a time by 1275 LDLT/DDLT interaction. As a second step, HCV disease severity will be added to the 1276 model to see if viral level is significantly predicted by disease severity. Fourth, the 1277 incidence of cholestatic hepatitis in LDLT and DDLT will be compared using logistic 1278 regression, adjusted for any other prognostic factors. Finally, graft and patient survival 1279 will be analyzed using Kaplan-Meier estimators, logrank tests comparing LDLT and 1280 DDLT, and Cox regression to compare groups adjusted for other variables.

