357 358 359 360 361 362 363	After obtaining the subject's informed consent for participation in the study, the following assessments will be performed according to the visit schedule. Subjects recruited from the A2ALL Retrospective Study will join the cohort visit schedule from whatever clinical point they are at in their transplant or donation experience. Exceptions to this would be informed consent assessments for donors and protocol biopsies for subjects who are undergoing treatment for recurrent HCV post-transplant. Tables summarizing the visit schedules for donors and recipients with accompanying tests and procedures are included as Appendices A and B.
366 367 368	Since the study is primarily an observational investigation, it should be remembered that many of the assessments listed below are included in what is considered standard of clinical care in many institutions, and therefore would not require additional visits or sample collections from the patient.
	Enrollment – Recipients:
373 374 375 376 377 378 379 380 381 382 383 384 385 386 387 388	
 
Medical history
 
Social history
 
Demographic information
 
Physical examination: including weight, blood pressure, etc.
 
Routine laboratory assessment: blood will be drawn to obtain values for the following tests: multichannel automated liver function tests, serum sodium, AFP, albumin, creatinine, and coagulation panels
 
Blood sample will be drawn for HLA typing
 
Blood sample for NIDDK Biosample Repository
 
Whole blood for NIDDK Genetics Repository
 
Quality of life baseline assessment
 
HCV-infected subjects will undergo the following laboratory assessments in addition to those listed above: 
 
HCV RNA quantitative or qualitative assay
 
HCV genotype (if not done previously)
 
 
 
Subjects with HCC will also undergo the following imaging studies if not done within
 

389 390 391	
 
3 months previous to study enrollment:
 
o Bone scan
 
o Chest CT
 

392	
 
Abdominal MRI/contrast CT
 

393	
394	Pre-transplant Interval Assessments – Recipients:
395	
396	The following assessments will be performed quarterly from the time of enrollment until
397	transplant (or subject death if it occurs prior to transplant):
398	
399	• Physical examination: including weight, blood pressure, etc.

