468 469 470 471 472 473 474 475 476 477	
 
Physical examination: including weight, blood pressure, etc.
 
Routine laboratory assessment: blood will be drawn to obtain values for the following tests: multichannel automated liver function tests, serum sodium, albumin, AFP, creatinine, and coagulation panels
 
Blood sample for NIDDK Biosample Repository
 
Quality of life interval assessments at 3, 6, and 12 months and annually thereafter
 
Liver MRI/contrast CT at Month 3 only.
 
Recipients of a DDLT from an HCV-antibody positive donor must have HCV genotyping done at 3 months post-transplant
 

478 479	Post-transplant Interval Assessments – HCV-infected Recipients:
480	In addition to the assessments listed above, HCV-infected recipients will undergo the following assessments at the following time points:

483	• Week 1, Month 1, Month 3, Year 1, 2, and 3: HCV RNA quantitative or qualitative
484	analysis
485	• Month 3, Year 1, 2 and 3: Liver biopsy
486	• Month 3, Year 1, 2 and 3: Tissue sample for NIDDK Biosample Repository
487	
488	Post-transplant Interval Assessments – Subjects with HCC:
489	
490	In addition to the assessments listed above for all recipients, recipients with HCC will
491	undergo the following assessments at Months 6, 12, 18 and 24:
492	
493	• Serum AFP (at month 18 in addition to AFP's done at interval assessments for all
494	recipients)
495	• Abdominal MRI/contrast CT: at months 6, 12 and 24 only.
496	
497	Subjects Showing Signs and Symptoms of Allograft Rejection:
498	
499	Subjects showing signs and symptoms of allograft rejection will undergo a liver biopsy
500	with analysis to confirm the diagnosis of rejection. A biopsy will be performed to
501	confirm each rejection episode. A tissue sample from these biopsies will also be sent for
502	storage at the NIDDK Biosample Repository.
503	
504	Post-Donation Assessments – Donors:
505	
506	The following assessments will be performed for donors at Week 1, and Months 1, 3, and
507	12, and annually thereafter until the study is complete or the donor reaches a study
508	endpoint or is lost to follow-up:
509	
510	• Routine laboratory assessment: blood will be drawn to obtain values for the
511	following tests: multichannel automated liver function tests, albumin, creatinine,
512	coagulation panels, white blood cell count, hemoglobin, ferritin, platelets, BUN
513	Blood sample for NIDDK Biosample Repository
514	• Liver MRI/contrast CT at month 3 only

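### HCV fibrosis and Knodell slopes are compared without separating values before and after antiviral start, although reaching the progression endpoint is what permits antiviral therapy, so effective treatment would shrink the LDLT–DDLT slope difference

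*Protocol*

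**What the plan says.** Protocol section 4.5.1 states: "Antiviral therapy will not be used until the patient achieves a level of significant disease", and the sentence goes on to a "severity that has been defined by four histological endpoints with/without clinical criteria". The Primary Endpoint list defines progressive disease by four criteria. Three are built on the Ishak score, alone or with bilirubin or the Knodell score, and the fourth is cholestatic hepatitis.

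The visit schedule in section 4 sets, for HCV-infected recipients, "Month 3, Year 1, 2 and 3: Liver biopsy". HCV RNA is also scheduled to Year 3.

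Section 4.5.5 states of the Ishak slope and the necroinflammatory score: "Knodell score) will be analyzed using repeated measures regression". It tests the difference in slopes with "an interaction term between LDLT/DDLT and follow-up time". It models viral level in the same way, at day 7 and months 1, 3, 6 and 12. None of these analyses mentions antiviral therapy. Section 4.5.4 states 82% power for a slope difference of 0.10 per year.

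Section 4 makes an exception to the visit schedule for "protocol biopsies for subjects who are undergoing treatment for recurrent HCV post-transplant". It is written for subjects recruited from the Retrospective Study, and the HCV eligibility criteria repeat it for subjects who join after transplant. Section 4.5.3 lists post-operative HCV recurrence and treatment data among the items collected.

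**The concern.** Treatment becomes permissible because of the variable under analysis. If LDLT recipients progress faster, which is the difference the aim is powered to detect, they qualify for therapy more often and earlier. Their later biopsies then partly describe the drug and not the graft. A slope fitted through both periods mixes the two, and the mixture differs between the groups. The fibrosis comparison could then show a small or non-significant difference where a real one exists, and the 82% power quoted for it would be misleading.

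**Working it through.** **Inputs from section 4.5.4.** There are 108 LDLT and 107 DDLT patients, with two-sided alpha 0.05. The yearly slope is 0.45 for DDLT against 0.55 for LDLT, with SD 0.25. The endpoint is reached by 10% (DDLT) and 25% (LDLT) at 1 year, and by 50% and 70% at 3 years.

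**Reproducing the plan's power.** SE = 0.25 × √(1/107 + 1/108) = 0.0341. Power = Φ(0.10/0.0341 − 1.96) = Φ(0.97) = 83.5%; the noncentral t gives 83.1%. The plan states 82%, so its figure is reproduced. The two composite comparisons also reproduce: 83.0% (stated 82%) and 85.4% (stated 85%).

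**Follow-up time after the endpoint.** Taking the proportions as linear between the stated points, over 3 years:
- LDLT: (0.125 + 2 × 0.475)/3 = 0.358
- DDLT: (0.05 + 2 × 0.30)/3 = 0.217

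**Hand approximation.** Observed slope ≈ planned slope × (1 − share × uptake × effect). With half treated and fibrosis stopped:
- LDLT: 0.55 × (1 − 0.358 × 0.5) = 0.452
- DDLT: 0.45 × (1 − 0.217 × 0.5) = 0.401
- Difference: about 0.05

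All treated with progression halved gives the same product, and so the same difference.

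**Simulation on the actual biopsy times.** Biopsies fall at 0.25, 1, 2 and 3 years, with a least-squares slope per patient. Therapy starts at the visit where the endpoint is reached. Year 2 proportions are interpolated (30% and 47.5%). The true difference is 0.10 and all biopsies are kept. Ranges cover endpoint timing that is unrelated, moderately related or fully related to the patient's own slope. Power is for a significant result in the true direction.

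| Uptake among eligible patients | Slope after therapy | Observed difference | Power |
|---|---|---|---|
| any | unchanged | about 0.10 | 83–85% |
| half | halved | 0.074 to 0.079 | 65–71% |
| half | stopped | 0.048 to 0.058 | 35–37% |
| all | halved | 0.049 to 0.059 | 44–58% |
| all | stopped | −0.003 to 0.017 | 2–7% |
| half | regressing at half the former rate | 0.023 to 0.038 | 9–16% |
| half | regressing at the full former rate | −0.002 to 0.017 | 2–6% |
| all | regressing at half the former rate | −0.054 to −0.024 | under 1% |

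Uptake and drug effect are assumptions, because the protocol gives neither.

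**Viral level.** The model in 4.5.5 ends at month 12, when at most 25% and 10% could be on therapy. For an assumed mean fall of 1 to 4 log in treated patients, the spurious shift is at most (0.25 − 0.10) × 1 to 4 = 0.15 to 0.60 log lower in LDLT, at that one visit. This is an upper bound, since a patient who first qualifies at the Year 1 biopsy would generally start therapy after the month-12 sample. Section 3.5 and the Secondary Endpoints also list months 24 and 36. With full uptake and an assumed 2-log fall, the month-36 shift would be (0.70 − 0.50) × 2 = 0.40 log.

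**The proposed analysis.** In simulation, a likelihood-based mixed model on values up to antiviral start recovered about 0.09 to 0.105 of the true 0.10, with power near 70%. Keeping all values gave 0.01 to 0.056, with power of about 13% to 43%. These power figures depend on the assumed biopsy-to-biopsy variability, which the protocol does not give.

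**The case against.** The strongest reply is that 4.5.5 is silent and not wrong. It never says that on-treatment values are kept, and such rules often sit in a statistical analysis plan, which is not at hand. The background to section 4.5 also promises control for factors that affect progression, in an open list. This has some weight, but the protocol itself ties treatment to the outcome, chooses the slope test and states its power with no allowance for treatment. Adding therapy as an ordinary covariate would not repair it, because therapy is a consequence of earlier outcome values.

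A second reply is that comparing grafts under one common treatment rule is a legitimate question. It is, but withholding therapy until progression points to the untreated course as the interest of this aim, and a slope diluted by therapy does not measure that. The all-values analysis still has a place as a sensitivity analysis.

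Three stronger readings are tempting, and the document supports none of them:
- **The slope difference is erased or reversed.** Section 4.5.1 permits therapy without requiring it. Erasure needs near-full uptake with arrest, or half uptake with full regression. Reversal needs wide uptake with regression.
- **The primary progression comparison is compromised.** The endpoint is reached before therapy is permitted, so the logistic and discrete-time analyses of first progression are largely untouched.
- **The planned viral-level model is badly distorted out to month 36.** That model stops at month 12.

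The biopsy exemption does not remove the problem. It covers only subjects from the Retrospective Study or those joining after transplant, and for them it replaces on-treatment values with missing ones.

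**Conclusion.** The point holds for the secondary Ishak and Knodell slope comparisons. As written, any effective antiviral therapy attenuates the LDLT–DDLT difference, and the 82% power applies only if therapy is unused or has no effect on fibrosis. For the two middle scenarios (half treated with fibrosis stopped, or all treated with progression halved), a true 0.10 per year is seen as about 0.05 to 0.06, with power of roughly 35% to 58%. The direction of the bias rests on the protocol's own endpoint proportions; its size rests on assumed uptake and drug effect. The effect on the month-12 viral-level model is small and confined to early progressors, but it would matter for the viral levels listed at months 24 and 36.

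**What to change.** In section 4.5.5, make the main Ishak-slope, Knodell and viral-level analyses likelihood-based mixed models on measurements up to the start of antiviral therapy, including the biopsy at which the patient qualified. Report the analysis of all values as a sensitivity analysis. State that a patient treated after meeting the endpoint remains counted as progressed in the yes/no and discrete-time analyses.

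This is a change of wording. Treatment data are already listed in section 4.5.3, but it should be confirmed that the form captures the antiviral start date. The price is fewer late biopsies: with full uptake, up to 47.5% of LDLT and 30% of DDLT patients (interpolated) would lose the Year 3 value. Power would then be about 70% and not 82%, and section 4.5.4 should say so. The approach also relies on the start of treatment being explained by the recorded biopsy and laboratory values. No change to clinical management is proposed.
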